#### 6.4.4 Vital Signs

Vital signs will be assessed pre-dose at the timepoints detailed in the Schedule of Assessments (Table 1). The following vital signs will be measured:

- Blood pressure (supine) (systolic and diastolic [mmHg])
- Orthostatic blood pressure (systolic and diastolic [mmHg]))
- Heart rate (bpm)
- Body temperature (°C) (oral, tympanic, temporal, or forehead infrared)
- Respiratory rate (breaths per minute)

Supine BP and HR recordings will be made after the subject has been supine for at least 5 minutes.

Orthostatic blood pressure will be recorded as specified in Table 1. The first blood pressure will be the average of 3 measurements recorded after the subject is supine for 5 minutes; the second blood pressure will be recorded after the subject has stood for up to 3 minutes. A drop in blood pressure of  $\geq$  20 mmHg, or in diastolic blood pressure of  $\geq$  10 mmHg will be considered abnormal.

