- k Vital signs (systolic and diastolic BP, orthostatic BP, HR, respiratory rate, and body temperature) will be performed pre-dose on all visits. Supine BP and HR recordings will be made after the subject has been supine for at least 5 minutes. Orthostatic BP will be recorded as follows: the first blood pressure will be the average of 3 measurements recorded after the subject is supine for 5 minutes; the second blood pressure will be recorded after the subject stood for up to 3 minutes.
- 1 Safety labs include chemistry, hematology, urinalysis, and coagulation.
- m Prior and concurrent medications.
- n Subject hearing will be tested to establish suitability for ERP assessment (ability to hear or differentiate the 2 different tones necessary for auditory ERP P300 assessment, using the centrally provided ERP equipment); subjects who wear a hearing aid must remove their hearing aid during the Screening auditory test and during ERP P300 recordings.
- o ERP P300 will be performed at the Pre-baseline visit (Visit 2a, Day -10 to Day -3, no dosing); pre-dose and post-dose at Baseline/Day 1 (Visit 2b), Week 2 (Visit 3), Week 12 (Visit 5), and Week 26 (Visit 8). ERP P300 data should be uploaded for quality check immediately after the completion of the Pre-baseline visit (Visit 2a). ERP P300 will also be performed at Safety follow-up (Visit 9, no dosing).
  - Pre-dose ERP P300 assessments will be performed immediately preceding IMP dose but can be up to 1 hour before dose
    in clinic.
  - Post-dose ERP P300 assessments will be performed at approximately 2 (± 1) hours after dose.
- r Subjects who terminate prior to Visit 9 are to complete same assessments as Visit 8/ET (early termination). For clinical outcome assessments, if completed the assessment within 4 weeks of the ET visit they do not need to be repeated; all safety outcomes and drug accountability should be performed regardless of interval.
- \* At Baseline/Day 1 (Visit 2b), ADAS-Cog13 will be performed pre-dose. For visits after Baseline (except for Safety follow-up when dosing is not applicable), all cognitive assessments will be performed post-dose, in the order of ADAS-Cog13, assessments, with ADAS-Cog13 performed at approximately 1 hour (± 30 minutes) post dose.

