Study drug will be administered by SC injection OD preferably during daytime; subjects must not take another dose within 8 hours of the preceding dose. The first SC injection of study drug will be performed on site under supervision. The subject should withhold study drug administration on the day of subsequent clinic visits; study drug administration will be done on site under supervision of site staff at these visits. Each subject is required to have a primary caregiver willing to accept responsibility for supervising or, if required, administering study drug, and assessing the condition of the subject throughout the study in accordance with all protocol requirements. During the double-blind treatment period, clinic visits will take place on Day 1 and thereafter at Weeks 2, 6, 12, 16, 20, and 26, with a safety follow-up visit scheduled 4 weeks after completion of the double-blind period at Week 30 (see Table 1 for Schedule of Assessments). On Day 1, after completion of the first dose, subjects will remain on-site for 2 hours for post-treatment clinical observation.

ADAS-Cog13, and assessments shall occur at clinic visits in the morning at approximately the same time they were performed during the initial baseline assessment (Visit 2b). Subjects will undergo post-baseline ERP P300 assessments at clinic visits (pre- and/or post-dose timepoints) as specified in Table 1.

Subjects may live at home, in a senior residential setting, or an institutional setting without the need for continuous nursing care, and should not be likely to experience a change in living conditions (e.g., institutionalization, moving to a different city, etc.), or change in primary caregiver, during participation in the trial period. The end of the study is defined as the date of the safety follow-up visit, Visit 9/Week 30. Subjects who terminate prior to Visit 8 are to complete the same assessments as Visit 8/early termination (ET).

Blood draws will take place at scheduled clinic visits for analysis of plasma concentrations of ATH-1017 (pro-drug) and ATH-1001 (active metabolite) (see Table 1 for Schedule of Assessments).

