## 6.4.6 12-Lead Electrocardiogram

Standard safety 12-lead ECGs will be performed at Screening, at pre-dose and 30 ( $\pm$  15) minutes post-dose on Day 1 and 30 ( $\pm$  15) minutes post-dose at all other visits. All ECGs will be performed in triplicate, as detailed in the Schedule of Assessments (Table 1).

The 12-lead ECGs will be performed after the subject has been resting supine for  $\geq 5$  minutes. The ECG will include all 12 standard leads and a Lead II rhythm strip on the bottom of the tracing. The following ECG parameters will be collected: PR interval, QRS interval, RR interval, QT interval, and QTcF.

All ECGs must be evaluated by the investigator or qualified designee for the presence of abnormalities. Collection and analysis of ECG data will be performed by a central ECG vendor.

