## 8.4 Safety Summaries

The Safety population will be used for analyses of each of the safety endpoints. All concomitant medications will be tabulated according to drug class and preferred term using the World Health Organization Drug dictionary. Clinical laboratory tests, vital signs, physical and neurological examinations, and ECG results will be summarized by number of subjects, frequency rates and by treatment group. The timepoint of each event will also be summarized.

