#### 6.4.4 Vital Signs

The following vital signs will be measured:

- Blood pressure (supine) (systolic and diastolic [mmHg])
- Orthostatic blood pressure (systolic and diastolic [mmHg])
- Heart rate (bpm)
- Body temperature (°C) (oral, tympanic, temporal, or forehead infrared)
- Respiratory rate (breaths per minute)

Supine BP and HR recordings will be made after the subject has been supine for at least 5 minutes. The assessment will be performed as per Appendix 2 Schedule of Assessment. The first blood pressure will be the average of 3 measurements recorded after the subject is supine for 5 minutes; the second blood pressure will be recorded after the subject has stood for up to 3 minutes. A drop in blood pressure of  $\geq$  20 mmHg, or in diastolic blood pressure of  $\geq$  10 mmHg will be considered abnormal.

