## 10.6.4 Vital Signs

Each vital sign will be summarized by treatment and by visit, using descriptive statistics (n, mean, median, SD, minimum, maximum) for the safety population for diastolic blood pressure, systolic blood pressure for both standing and supine position, heart rate and respiratory rate.

The latest non-missing vital sign value collected prior to dosing will be used as the baseline values. The baseline values will usually be the vital signs recorded at the baseline visit. In the case of repeated vital signs, the last collected values within that visit will be used for the summary tables.

Vital signs will be provided in a data listing by treatment group, subject, visit and parameter.

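### The SAP never counts the orthostatic drop that both documents define as abnormal, and its vital-sign tables can describe pre-dose readings only

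*Protocol*

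**What the plan says.** Vital signs are named in the primary safety endpoint (Protocol Section 2; SAP Table 1).

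- **Timing.** Protocol 6.4.4: "Vital signs will be assessed pre-dose at the timepoints detailed in the Schedule of Assessments (Table 1". Footnote k to Protocol Table 1, repeated in SAP Appendix 2: "Vital signs (systolic and diastolic BP, orthostatic BP, HR, respiratory rate, and body temperature) will be performed pre-dose on all visits". On visit days the home dose is held back (Protocol Section 3): "The subject should withhold study drug administration on the day of subsequent clinic visits".
- **Definition.** Protocol 6.4.4 and SAP 6.4.4 take the average of three supine readings as the first pressure; then "the second blood pressure will be recorded after the subject has stood for up to 3 minutes". A drop of at least 20 mmHg, or of at least 10 mmHg diastolic, counts as abnormal.
- **Outputs promised in the Protocol.** Section 8.4, in a sentence whose subject includes vital signs, ends: "ECG results will be summarized by number of subjects, frequency rates and by treatment group". Section 8.4.2 covers laboratory parameters and vital signs by visit, then promises counts of high and low values against the normal range, and shift tables.
- **Outputs planned in the SAP.** Section 10.6.4 gives n, mean, median, SD, minimum and maximum by treatment and visit for "diastolic blood pressure, systolic blood pressure for both standing and supine position, heart rate and respiratory rate", plus a subject-level listing. Where a vital sign is repeated within a visit, the last value collected is used.
- **Early stopping.** The note in SAP Section 6 keeps safety listings and summaries as they had been planned and makes only efficacy and biomarker analyses exploratory. SAP Section 8 says analyses will be minimal, but none of its bullets removes vital-sign frequencies.

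**The concern.** A criterion that is defined in both documents and measured at every dosing visit has no planned table. The Protocol treats low pressure as relevant to eligibility (exclusion 16 includes symptomatic hypotension), so a reader of the report will want to know how many subjects per arm met the criterion. Under SAP 10.6.4 that number does not appear. Body temperature is also measured (Protocol 6.4.4, SAP 6.4.4) but is missing from the list of summarised variables.

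A second, separate matter is interpretation. Because every scheduled pressure is taken before that day's dose, an unremarkable set of tables could be taken as showing that the drug does not affect blood pressure, when pressure after a dose was never scheduled.

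**Working it through.** The documents give no figure for blood pressure, so there is none to reproduce. The check has four steps.

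**1. Follow the criterion from definition to output.** It is defined in Protocol 6.4.4 and SAP 6.4.4. SAP 10.6.4 contains no supine-to-standing difference and no category count. The high/low counts in Protocol 8.4.2 would not supply it even if carried over, because they compare single values with a normal range rather than measuring a within-subject change. The only remaining route is to derive it by hand from the listing.

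**2. Can the count be read from the planned statistics?** Write D for supine minus standing systolic pressure. If the same subjects have both readings, mean(D) = mean supine − mean standing, so the mean drop is recoverable. The spread is not: Var(D) = Var(supine) + Var(standing) − 2 × Cov(supine, standing), and the tables do not give the covariance. Two arms can therefore match on every tabulated mean and SD and still differ in the share meeting the criterion.

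Illustration, with assumed values and D taken as normal with mean 8 mmHg: P(D ≥ 20) = 1 − Φ((20 − 8)/SD).

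- SD 10: 1 − Φ(1.2) = 0.115, or 0.115 × 25 = 2.9 subjects in a planned arm of 25
- SD 15: 1 − Φ(0.8) = 0.212, or 5.3 subjects
- SD 20: 1 − Φ(0.6) = 0.274, or 6.9 subjects

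**3. What could the count show?** At the planned 50 pooled active against 25 placebo (two-sided 5%, assumed rates), power is about 40% for 20% against 40%, and about 73% for 20% against 50%. Enrolment stopped early, so the real figures would be lower. The table would be descriptive, as the Protocol intends for all safety data.

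**4. Timing, side by side, at the seven in-clinic dosing visits (2b and 3 to 8).**

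- Blood pressure: post-dose at 0 of 7 (footnote k)
- ECG: 30 ± 15 minutes post-dose at 7 of 7 (footnote j)
- ADAS-Cog13: about 1 hour post-dose at Visits 3, 5, 7 and 8
- P300: about 2 hours post-dose at Visits 2b, 3, 5 and 8, as well as pre-dose

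The Day 1 pre-dose reading precedes any drug, and Visit 9 has no dosing. The two-hour Day 1 observation (Protocol 5.5) and the physical and neurological examination (6.4.7) specify no blood pressure. Unscheduled visits (7.1.1) leave vital signs to the investigator.

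How far the pre-dose readings lie from peak exposure cannot be established. No time of peak or half-life is given, and the only stated interval is a minimum: "subjects must not take another dose within 8 hours of the preceding dose". Taking 0.5^(t/half-life) with assumed half-lives of 1 to 12 hours, the fraction of peak remaining runs from about 0% to 25% at 24 hours (0.5^(24/12) = 0.25) and from about 0.4% to 63% at 8 hours (0.5^(8/1) = 0.004; 0.5^(8/12) = 0.63).

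**The case against.** **The case for leaving the plan alone.** The documents report no pressure signal: Protocol 1.3 describes the earlier dosing as well tolerated and names injection-site reactions and a nonclinical liver risk, not hypotension. Standing pressure is summarised by arm and visit, the mean drop can be obtained by subtraction, and individual drops can be worked out from the listing. With few subjects, a count will be imprecise. SAP Section 8 also warns that analyses will be minimal.

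Much of this is right, and it limits the weight of the point. It does not remove it: the mean drop is not the number meeting the criterion, and a listing is not a summary. The warning in Section 8 sits beside a note in SAP Section 6 that keeps the safety summaries.

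**Stronger readings that a reader might infer, which the documents do not support:**

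- *That the missing table is why an effect near peak exposure cannot be seen.* It is not. That limit comes from the timing alone; a count in pre-dose data would not lift it.
- *That the readings are taken about 24 hours after the last dose, or that other measures are post-dose because the prodrug converts rapidly.* Neither is stated. Dosing is preferably in daytime with an 8-hour minimum gap, and the conversion is described without being given as the reason for any assessment time.
- *That a post-dose fall would go unnoticed unless the subject volunteered it.* Physical and neurological examinations are post-dose at dosing visits (Table 1, footnote h), staff also elicit adverse events by examination and open questions (Protocol 6.4.1.2), and Day 1 has two hours of observation. These could catch symptoms, but none is a scheduled pressure measurement.

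**Conclusion.** The point holds in two separate parts.

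1. **Tabulation.** A defined criterion within a primary safety endpoint has no planned count, although the Protocol promises frequencies for vital signs and the SAP says safety summaries are retained. The omission is not specifically listed as a change. It follows from the text and needs no assumption. The 12% to 27% range shows only why means do not replace a count; its mean, SDs and normal shape are assumed. The Protocol does not name a table of the orthostatic drop, so the gap is between a defined criterion with general promises of frequencies and an output that delivers neither.
2. **Timing.** With no post-dose blood pressure at any of the seven dosing visits, the tables describe pre-dose readings. They could show a sustained pre-dose effect but cannot exclude a post-dose fall. This limits what may be concluded; it is not evidence that such a fall occurs.

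The first part should be corrected before the tables are produced. The second can now only be disclosed. Neither undermines the safety analysis as a whole.

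**What to change.** **In SAP 10.6.4:**

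- First settle two points in the definition. Reconcile the average of three supine readings (6.4.4) with the rule that takes the last value collected (10.6.4), and state which pressure the 20 mmHg drop refers to, since only the 10 mmHg limb names one.
- Derive supine minus standing systolic and diastolic change per subject and visit, and tabulate n (%) meeting the criterion already defined, by arm and visit and at any post-baseline visit.
- Add a treatment-emergent count that excludes subjects who met the criterion at baseline.
- Summarise body temperature.

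The cost is SAP wording, one derived variable, one table for the drop and a routine summary of temperature, all from data already collected.

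**In the study report:** state that all scheduled vital signs were pre-dose and that the tables do not bear on blood pressure after a dose. The cost is one sentence.

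**For a similar protocol only:** record a supine and standing set beside the 30-minute post-dose ECG, where the subject is already lying down ("The 12-lead ECGs will be performed after the subject has been resting supine for" at least 5 minutes), and compare it with the pre-dose set from the same visit, so that an acute change is not mixed with time on study. The ECG window (15 to 45 minutes) overlaps the ADAS-Cog13 window (30 to 90 minutes), so the order must be fixed to leave the cognitive test undisturbed. The cost is a few minutes per visit and no extra visit.

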#### 6.4.5 *Weight*

Weight will be measured at Screening (for calculation of BMI as part of the eligibility criteria), at Baseline/Day 1 (Visit 2b), Visit 5 (Week 12), Visit 8 (Week 26), and Visit 9 (Safety follow-up).

## 6.4.6 12-Lead Electrocardiogram

Standard safety 12-lead ECGs will be performed at Screening, at pre-dose and 30 ( $\pm$  15) minutes post-dose on Day 1 and 30 ( $\pm$  15) minutes post-dose at all other visits. All ECGs will be performed in triplicate, as detailed in the Schedule of Assessments (Table 1).

The 12-lead ECGs will be performed after the subject has been resting supine for  $\geq 5$  minutes. The ECG will include all 12 standard leads and a Lead II rhythm strip on the bottom of the tracing. The following ECG parameters will be collected: PR interval, QRS interval, RR interval, QT interval, and QTcF.

All ECGs must be evaluated by the investigator or qualified designee for the presence of abnormalities. Collection and analysis of ECG data will be performed by a central ECG vendor.

## 6.4.7 Physical and Neurological Examination

Physical and neurological examination will be performed by the investigator or designee at the timepoints detailed in the Schedule of Assessments (Table 1).

The physical examination includes an assessment of general appearance and a review of systems (dermatologic, head, eyes, ears, nose, mouth/throat/neck, thyroid, lymph nodes, respiratory, cardiovascular, gastrointestinal, extremities, musculoskeletal, neurologic, and psychiatric systems).

Body weight (kg) and height (meters) will be assessed at Screening. Body weight and height will be used to calculate BMI using the following formula: weight (kg)/[height (m)].

Neurological components include, but are not limited to, the following assessments: mental status, cranial nerves, muscle strength, tone, and bulk, reflexes, coordination, sensory function, and gait.

## 6.4.8 Columbia-Suicide Severity Rating Scale (C-SSRS)

The C-SSRS will be performed at Screening, Baseline/Day 1 (Visit 2b), Visit 3 (Week 2), Visit 4 (Week 6), Visit 5 (Week 12), Visit 6 (Week 16), Visit 7 (Week 20), Visit 8/ET, and Visit 9 (Safety follow-up) (Week 30) (Table 1). The C-SSRS supports suicide risk assessment through a series of simple, plain-language questions. The responses assist in identifying whether a subject is at risk for suicide, assesses the severity and immediacy of that risk, and gauge the level of support that the subject may require. If items 1 to 5 of the C-SSRS have a positive response and are of clinical concern, as judged by the investigator during the study, the Medical Monitor must be contacted.

## 6.4.9 Geriatric Depression Scale (GDS)

The GDS is a self-report measure of depression in older adults with a "Yes/No" response format. The GDS was originally developed as a 30-item instrument. It has since been validated in a shortened form comprising 15 items (Sheikh, 1986). The total score range is 0 to 15, with a higher score indicating more severity. A GDS score of  $\leq 7$  is required at Screening. In discussion with the Medical Monitor, subjects with a GDS score between 8 and 10 inclusive can be considered for study participation if the increased score is driven by specific domains related to the pandemic and its restrictions, rather than by major depression.

GDS assessments will be performed at Screening, Visit 2b (Baseline/Day 1), Visit 5 (Week 12), Visit 8/ET (Week 26), and Visit 9 (Safety follow-up).

# 6.6 Genotyping

Blood sample(s) will be collected at Screening for analysis of GBA genotype in subjects who consented to genotyping.

#### 7 STUDY CONDUCT

- Study procedures and their timing are summarized in the Schedule of Assessments (Table 1).
- Protocol exemptions related to enrollment criteria are only allowed with prior investigator, Medical Monitor, and Sponsor approval, supported by documented agreement from the IRB/IEC.
- Immediate safety concerns should be discussed with the Sponsor immediately upon occurrence or awareness to determine if the subject should continue or discontinue study treatment.
- Adherence to the study design requirements, including those specified in the Schedule of Assessments, is essential and required for study conduct.
- All screening evaluations must be completed and reviewed to confirm that potential subjects meet all eligibility criteria. Screening procedures may be conducted on up to 2 separate dates if necessary to accommodate subject and study center schedule. However, every effort should be made to conduct all procedures as early as possible in the screening period. The investigator will maintain a screening log to record details of all subjects screened and to confirm eligibility or record reasons for screening failure, as applicable.
- Due to the quantitative functional biomarker nature of this study, particular precautions will have to be implemented at each site for the electrophysical assessments, i.e. availability of a dedicated quiet EEG room with controlled lighting and temperature.

#### 7.1 Schedule and Order of Assessments

The study will consist of up to 28 days of Screening (Day -32 through Day -4), a Pre-baseline visit (Visit 2a, Day -10 to Day -3), Baseline (Visit 2b, Day 1, randomization), followed by 26 weeks of double-blind treatment, and a 4-week safety follow-up. Note: if 28 days is not sufficient to complete the screening period, the possibility of an extension can be discussed with the Medical Monitor.

All assessments to be performed during the study are detailed by visit/timepoint in Table 1. For clinical outcome assessments evaluating subject's cognitive condition, the general order should be followed:

- (1)
- (2) ADAS-Cog13
- (3)
- (4) ERP P300 assessments

All cognitive assessments including MMSE, ADAS-Cog13, and shall occur at clinic visits in the morning, in the specified order when applicable.

ADAS-Cog13 assessments will be performed pre-dose at Baseline/Day 1 (Visit 2b), and post-dose at approximately 1 hour (± 30 minutes) at Week 2 (Visit 3), Week 12 (Visit 5), Week 20 (Visit 7), and Week 26 (Visit 8).

The order of assessments and timing for all other endpoints are flexible.

